Study Design	
This is a phase II study of acalabrutinib in combination with R-ICE in rel/ref non-GC DLBCL per Hans criteria. Each cycle will begin day 1 and last for 21 days. Acalabrutinib will be administered day 1-21 of every cycle for 3 cycles, in conjunction with 3 cycles of R-ICE. R-ICE will be administered per standard institutional policy.
 
In addition to a baseline PET-CT scan, confirmatory scans will be obtained post cycle 2 per cross sectional imaging criteria by CT and post cycle 3 per RECIL criteria. If patients have progressive disease after cycle 2, they will be removed from study treatment.
 
An EOT (EOT) visit within 14 days of the last dose of study drug is required for any patients who permanently discontinue study drug for any reason, including disease progression. Patients will then be followed for 52 weeks for EFS, PFS, and OS after removal from or completion of study treatment, or until death, whichever occurs first. Patients removed from study treatment for adverse events will be followed until resolution or stabilization of the adverse event.

Efficacy and Safety Parameters	
Efficacy Parameters EFS, PFS, OS
 
Safety Parameters The safety of acalabrutinib in combination with R-ICE will be characterized by the type, frequency, severity, timing of onset, duration, and relationship to study drug of any treatment emergent AEs or abnormalities of laboratory tests; SAEs; DLTs, or AEs leading to discontinuation of study treatment, or death.
 
For consistency of interpretation, AEs and laboratory results will be coded using the Medical Dictionary for Regulatory Activities (MedDRA), and the severity of AEs and selected laboratory parameters will be graded using the Common Terminology Criteria for Adverse Events (CTCAE), Version 5.0.

Pharmacodynamic, Pharmacokinetic and Biomarker Parameters	Exploratory correlative studies may include characterization of tumor subtypes by NGS, including comparing pre- and post- study treatment biopsies in patients without a clinical response and/or progression of disease.  Baseline and end of treatment (EOT) PET scan will be assessed for response by MTV as a correlative biomarker.

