## **3.4 STUDY INTERVENTION DISCONTINUATION AND PARTICIPANT DISCONTINUATION/WITHDRAWAL**

### **3.4.1 Discontinuation of Study Intervention**

Discontinuation from protocol treatment does not mean discontinuation from the study, and remaining study procedures should be completed as indicated by the protocol. If a clinically significant finding is identified (including, but not limited to changes from baseline) after enrollment, the Investigator or qualified designee will determine if any change in participant management is needed. Any new clinically relevant finding will be reported as an adverse event (AE).

The data to be collected at the time of study intervention discontinuation will include the data collected during the safety evaluation visit and follow-up information.

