### **3.4.2 Participant Discontinuation/Withdrawal from the Study**

Participants are free to withdraw from participation in the study at any time upon request. An Investigator may discontinue or withdraw a participant from the study for the following reasons:

- Pregnancy
- Significant study intervention non-compliance
- If any clinical adverse event (AE), laboratory abnormality, or other medical condition or situation occurs such that continued participation in the study would not be in the best interest of the participant
- Disease progression which requires discontinuation of the study intervention
- If the participant meets an exclusion criterion (either newly developed or not previously recognized) that precludes further study participation
- Participant unable to receive investigational treatment for 21 days/weeks.

The reason for participant discontinuation or withdrawal from the study will be recorded on the Case Report Form (CRF).

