Based on the specific adverse event observed, 1 dose level reduction is permitted for acalabrutinib (see Table below). If acalabrutinib is withheld for  $\leq$  1 week due to acalabrutinib-related toxicity; study drug should be resumed with a dose reduction when treatment resumes following recovery from the toxicity. If there is unacceptable toxicity despite 1 dose reduction the treatment should be discontinued. If treatment must be withheld for an acalabrutinib-related adverse event that fails to resolve to an acceptable level (eg,  $\leq$  Grade 1 nonhematologic toxicity) within 1 week after the date acalabrutinib was withheld, treatment with acalabrutinib should be permanently discontinued. In this event, the subject will be discontinued from the treatment, and End-of-Treatment Visit assessments will be performed including through the protocol-specified AE reporting window and have follow-up for ongoing SAEs to resolution or stability unless the subject lost to follow-up. (see section 6.2.6)

Acalabrutinib dose adjustments also apply to cycle 1.

**Acalabrutinib** dose will not be reduced for hematological toxicities unless the hematologic toxicities fail to recover by day 21 of a cycle.

The actions in the table below should be taken for the following toxicities at day 21 of the cycle:

- Grade 4 ANC (<500/ $\mu$ L) for  $>7$  days
- Grade 3 thrombocytopenia (<50,000/mcL) in the presence of clinically significant bleeding events
- Grade 4 thrombocytopenia (<25,000/mcL)
- Grade 3 or 4 nausea, vomiting, or diarrhea, if persistent, despite optimal antiemetic and/or anti-diarrheal therapy
- Any other Grade 4 or unmanageable Grade 3 toxicity.

For Grade 3 or 4 atrial fibrillation or persistent atrial fibrillation of any grade, consider the risks and benefits of acalabrutinib treatment. *If clinically indicated, the use of anticoagulants or antiplatelet agents may be considered for the thromboprophylaxis of atrial fibrillation.*

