### **3.12 REMOVAL FROM STUDY**

Reasons for removal of a subject from the study are:

- Subject's withdrawal of consent from study
- Decision by sponsor to terminate the study
- Subject lost to follow-up
- Death

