### **4.4 FOLLOW-UP FOR PROGRESSION AND SURVIVAL**

Patients will be followed every 12 weeks for 52 weeks for EFS and PFS after the EOT visit, removal from study, or until death, whichever occurs first. Follow up can include CBC, CMP, LDH and CT and/or PET/CT per standard of care. Patients removed from study for unacceptable adverse events will be followed until resolution or stabilization of the adverse event.

Patients who discontinue study treatment because of PD will enter overall survival (OS) follow-up and will be contacted every 12 weeks for 52 weeks for survival status.

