### **5.2.6 Secondary Efficacy Endpoint**

ORR and PR rates will be calculated along with exact 95% CIs based on binomial distribution. PFS is defined as the time from first dose to documented disease progression, or death from any cause, whichever occurs first. Data for subjects who are still alive and free from progression at the time of data cutoff date, lost to follow-up, or have discontinued the study will be censored on last assessment (or, if no post-baseline tumor assessment, at the time of first dose plus 1 day). Duration of PFS will be estimated using Kaplan-Meier methodology.

Approximate 95% CIs for median duration of PFS will be computed using the formula proposed by Brookmeyer and Crowley.

EFS is defined as the time from first dose to documented disease progression, death from any cause, or study dropout, whichever occurs first. Duration of EFS will be estimated using Kaplan-Meier methodology. Approximate 95% CIs for median duration of EFS will be computed using the formula proposed by Brookmeyer and Crowley.

OS is defined as the time from first dose to death from any cause. Data for subjects who are still alive at the time of data cutoff date, lost to follow-up, have discontinued the study (or, if no post-baseline assessment, at the time of first dose plus 1 day) will be censored. Duration of OS will be estimated using Kaplan-Meier methodology. Approximate 95% CIs for median duration of OS will be computed using the formula proposed by Brookmeyer and Crowley.

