f	Samples can be taken on the day of or day prior to dosing. The results do not need to be available before the dose of study drug is given.
g	Computed tomography and PET scans obtained for standard subject evaluations before signing ICF can be used for screening, but should not be older than 28 days prior to enrollment.
h	Computed tomography scan and PET scans will be performed at screening and at the end of Cycle 3. CT scan will occur Day 15-21 of Cycle 2 to demonstrate lack of progression of disease (PD)  . If PD, patient will be removed from study. Positron emission tomography scans must be done between Days 15 to 21 of Cycle 3.
i	Computed tomography and PET scans are required at early withdrawal. Computed tomography and PET scans performed after Cycle 3 are considered the End-of-Treatment disease efficacy assessment (or earlier if $< 3$ cycles administered as per investigator discretion). If early withdrawal prior to the end of Cycle 3, CT and PET scans are to be repeated.
j	Morphological and IHC examination of the bone marrow is required and should be performed within 28 days prior to the first dose of study drug. In subjects with bone marrow involvement prior to treatment, bone marrow biopsy must be repeated once during the study for confirmation of CR (preferentially within 30 days of initial documentation of CR). Bone marrow obtained for standard subject evaluations before signing ICF can be used for screening, but should not be older than 28 days prior to treatment.
k	If this visit occurs within 7 days of Cycle 1 Day 1. It may be used for the screening and Cycle 1 Day 1 treatment evaluations.
l	A directed physical exam, chemistry (potassium) and urinalysis assessments will be performed every day while participants are receiving R-ICE treatment.
m	RNB for patients with evaluable clonotype determined on pretreatment tumor specimen. Required ctDNA assessment time points: pre-treatment, and at EOT.
n	Follow-up every 12 weeks for 52 weeks after EOT visit, until removal from study, or until death. SAEs considered related to study drug should be documented
o	A patient diary will be provided to participants and study team members will advise participants on how to record information in the diary.

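### Section 3.4.2 lets investigators withdraw patients from the study for treatment-related reasons, so 1-year PFS and OS can be censored avoidably

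*Combined protocol and SAP*

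**What the plan says.** Section 3.4.2 lists six reasons for which an investigator may, but need not, withdraw a participant from the study. Four concern the course of treatment: an adverse event or other medical condition, significant non-compliance, progression requiring the intervention to stop, and "Participant unable to receive investigational treatment for 21 days/weeks". The other two are pregnancy and meeting an exclusion criterion. Section 4.2 and Appendix 1 footnote h also say that a patient with progression after cycle 2 is removed from the study. For the same event, the synopsis says removed from study treatment.

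Other sections keep the two kinds of stopping apart:

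- Section 3.4.1: "Discontinuation from protocol treatment does not mean discontinuation from the study".
- Section 3.8, on an acalabrutinib-related adverse event that has not resolved within one week: "In this event, the subject will be discontinued from the treatment, and End-of-Treatment Visit assessments will be performed".
- Section 3.11 withdraws patients from study treatment for confirmed progression, a changed medical condition, non-compliance, pregnancy, or toxicity beyond 28 days.
- Section 3.12, under "Reasons for removal of a subject from the study are", gives only consent withdrawal, sponsor termination, loss to follow-up and death.

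Section 5.2.6 says that PFS data for subjects who "have discontinued the study will be censored on last assessment". OS is censored on the same ground, and study dropout is an EFS event. Section 4.4 plans 12-weekly visits for 52 weeks "for EFS and PFS after the EOT visit, removal from study, or until death, whichever occurs first". Appendix 1 footnote n reads "Follow-up every 12 weeks for 52 weeks after EOT visit, until removal from study, or until death". The synopsis has patients "followed for 52 weeks for EFS, PFS, and OS after removal from or completion of study treatment".

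**The concern.** Section 5.2.6 makes leaving the study a censoring event for PFS and OS. A patient who has only stopped drug can still be observed for progression and death, and 3.4.1 intends that. If the investigator instead records a study withdrawal under 3.4.2, the outcome may go unobserved, and 5.2.6 censors it even if it was observed. The trigger is toxicity, non-adherence, inability to take drug, or progression, so the patients concerned may not share the prognosis of those who remain. Kaplan-Meier estimation assumes that they do. Section 3.4.4 does not replace treated patients who are withdrawn, so the information is not recovered.

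At stake are the 1-year PFS and OS estimates. EFS is also affected, because the same administrative choice may or may not create an event.

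**Working it through.** **Step 1. Compare the rules for each trigger.**

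| Trigger | Withdrawal from the study | Withdrawal from treatment only |
|---|---|---|
| Unable to receive drug | 3.4.2 | 3.8 for an unresolved acalabrutinib-related event; 3.4.1 in general |
| Adverse event or medical condition | 3.4.2 | 3.8, 3.11 |
| Non-compliance | 3.4.2 | 3.11 |
| Progression | 3.4.2, 4.2, Appendix 1 footnote h | Synopsis, 3.11 |

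None of these triggers is in 3.12. The conflict belongs to 3.4.2 as a whole, and the treatment-gap bullet is one instance.

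**Step 2. Unit of the treatment-gap bullet.** The course is 3 x 21 = 63 days. With two cycle delays of at most 7 days (3.8) it is 63 + 14 = 77 days. Twenty-one weeks is 147 days and could never act within the course, so only 21 days is workable. This is an editorial slip.

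**Step 3. Follow-up after leaving.** Section 4.4 treats removal from study as a point after which PFS and EFS follow-up runs. Footnote n treats it as the end of follow-up. Section 4.4 names OS contact only for patients who stop treatment because of progression. The synopsis covers OS for everyone, but after removal from treatment. Section 3.4.3 makes follow-up after withdrawal depend on the investigator asking and the patient agreeing.

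**Step 4. Effect of one early censoring.** Inputs: n = 46 (5.1), and 1-year PFS 0.62 and OS 0.65 from the phase I ibrutinib + R-ICE trial (1.2.3). Assumptions: no other censoring, and withdrawal before any other patient's event. The estimate then rests on the other 45 patients.

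- Censored patient would have had the event: change = S/45.
- Censored patient would have been event-free: change = -(1 - S)/45.

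| | Would have had event | Would have been event-free |
|---|---|---|
| PFS, S = 0.62 | 0.62/45 = +1.4 points | -0.38/45 = -0.8 points |
| OS, S = 0.65 | 0.65/45 = +1.4 points | -0.35/45 = -0.8 points |

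Check with whole patients for PFS: 29/46 = 63.0% becomes 29/45 = 64.4% (+1.4) or 28/45 = 62.2% (-0.8).

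For withdrawal at progression, the PFS event has already been recorded, so only OS is exposed.

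**Step 5. Several patients.** Let k patients be censored early, with true 1-year rate q. The estimate becomes (46S - kq)/(46 - k).

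- PFS, k = 2, q = 0.40: (28.52 - 0.80)/44 = 0.630, bias +1.0 point.
- PFS, k = 6, q = 0.20: (28.52 - 1.20)/40 = 0.683, bias +6.3 points.
- OS, k = 2, q = 0.40: (29.90 - 0.80)/44 = 0.661, bias +1.1 points.
- OS, k = 6, q = 0.20: (29.90 - 1.20)/40 = 0.718, bias +6.8 points.
- q = S: bias 0.

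Both k and q are assumed. The documents give neither.

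**Step 6. Scale.** The 95% half-width for PFS is 1.96 x sqrt(0.62 x 0.38/46) = 0.140. For OS it is 1.96 x sqrt(0.65 x 0.35/46) = 0.138.

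**Step 7. EFS.** If a withdrawal counts as study dropout and the patient would otherwise have been event-free, 1-year EFS falls by at most 1/46 = 2.2 points. If stopping treatment is already an event, nothing changes. Section 3.1.1 counts removal from study for any reason and 5.2.6 counts study dropout. Neither says whether stopping treatment is included.

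**The case against.** The best defence is that the plan already intends to keep these patients. Withdrawal under 3.4.2 is discretionary. Sections 3.7, 3.8 and 3.11 give most patients off drug a treatment-level rule, and 3.4.1 then keeps them in the study. Section 4.4 and the synopsis plan 52 weeks of follow-up, patients stopping for progression go into OS contact, and 3.4.3 allows outcome follow-up with consent. If removal from study in footnote n has its 3.12 meaning, a 3.4.2 withdrawal does not end follow-up. This stands as far as it goes: loss of data is possible, not certain. It does not remove the problem, because 5.2.6 as written censors anyone who has discontinued the study, whether or not data are collected afterwards.

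A reader might blame the treatment-gap bullet alone. The documents do not support that. The adverse-event bullet already reaches most patients who cannot take drug, and 3.12 omits all six of the 3.4.2 reasons. Deleting that one bullet would change little.

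A reader might also cite the phase I trial as a precedent for lost data. Section 1.2.3 describes at least 4 of 21 patients (19%) stopping early, 3 of 21 (14%) for reasons other than progression. None is described as a 21-day gap. One of those three was evaluable for survival by ITT, and the other two are reported progression-free. That trial shows outcomes being retained.

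**Conclusion.** The point holds as a minor, section-wide inconsistency. Sections 3.4.2 and 4.2 and Appendix 1 footnote h permit study-level withdrawal where 3.4.1, 3.11 and 3.12 do not, and 5.2.6 turns that withdrawal into censoring of PFS and OS. The censoring is avoidable and may be informative.

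The size is about +1.4 or -0.8 points per early-censored patient for 1-year PFS or OS. This rests on n = 46, the phase I rates and the simplifications in step 4. The number of such patients cannot be derived from the documents. It is probably small, and the half-width is about 14 points.

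Two stronger inferences are not supported. The first is that the estimates will be biased upward: the direction depends on the withdrawn patients' prognosis, and the bias is zero if it matches the rest. The second is that the trial's main conclusion is at risk. The CR rate and the Simon rule do not use the 5.2.6 censoring rules, treated patients who are withdrawn are not replaced (3.4.4), and Appendix 1 footnote i asks for CT and PET at early withdrawal. The affected estimates are secondary and carry no decision rule.

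**What to change.** - **3.4.2 and 3.11:** make the investigator-initiated reasons in 3.4.2 treatment-discontinuation rules under 3.11. Give the treatment-gap limit in days, consistent with 3.8; the investigators choose the value.
- **3.12:** state that only its listed reasons end study participation.
- **4.2 and Appendix 1 footnote h:** for progression, say removed from study treatment, as the synopsis does.
- **Appendix 1 footnote n:** align it with 4.4, so that all treated patients are followed for PFS and OS to 52 weeks unless they withdraw consent or are lost.
- **5.2.6:** censor PFS and OS only for consent withdrawal, loss to follow-up or data cutoff.
- **3.1.1 and 5.2.6:** use one term for the third EFS component and state whether stopping treatment counts as an event.

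The cost is a short wording amendment. No visits are added, because 4.4 already plans 12-weekly follow-up for 52 weeks. Sample size and decision rule do not change.

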### **3.4.3 Data Retention When Subjects Withdraw from FDA-Regulated Clinical Trials**

An investigator may ask a subject who is withdrawing whether the subject wishes to provide continued follow-up and further data collection subsequent to their withdrawal from the interventional portion of the study. Under this circumstance, the discussion with the subject would distinguish between study-related interventions and continued follow-up of associated clinical outcome information, such as medical course or laboratory results obtained through non-invasive chart review, and address the maintenance of privacy and confidentiality of the subject's information.

If a subject withdraws from the interventional portion of the study, but agrees to continued follow-up of associated clinical outcome information as described in the previous bullet, the investigator must obtain the subject's informed consent for this limited participation in the study (assuming such a situation was not described in the original informed consent form). In accordance with FDA regulations, IRB approval of informed consent documents would be required (21 CFR 50.25, 56.109(b), 312.60, 312.66, 812.100).

### **3.4.4 Participant Replacement Criteria**

Subjects who sign the informed consent form and are enrolled but do not receive the investigational treatment may be replaced. Subjects who sign the informed consent form, receive the protocol treatment, and subsequently withdraw, or are withdrawn or discontinued from the study, will not be replaced.

### **3.4.5 Screen Failures**

Screen failures are defined as participants who consent to participate in the clinical trial but are not subsequently entered in the study. Screen failures will be rescreened if they are eligible at a later time.

### **3.4.6 Lost to follow up**

A participant will be considered lost to follow-up if he or she fails to return for three scheduled visits and is unable to be contacted by the study site staff.

The following actions must be taken if a participant fails to return to the clinic for a required study visit:

- **For Missed Treatment Visits:** The site will attempt to contact the participant and reschedule the missed treatment visit as soon as possible and counsel the participant on the importance of maintaining the assigned visit schedule and ascertain if the participant wishes to and/or should continue in the study.
- **For Missed Post-Treatment Follow-Up Visits:** The site will attempt to contact the participant and reschedule the missed post-treatment follow visit within  $\leq 14$  days and counsel the participant on the importance of maintaining the assigned visit schedule and ascertain if the participant wishes to and/or should continue in the study.
- Before a participant is deemed lost to follow-up, the Investigator or designee will make every effort to regain contact with the participant (where possible, 3 telephone calls and, if necessary, a certified letter to the participant's last known mailing address or local equivalent methods). These contact attempts should be documented in the participant's medical record or study file.
- Should the participant continue to be unreachable, he or she will be considered to have withdrawn from the study with a primary reason of lost to follow-up.

## 3.5 STUDY DRUG

### 3.5.1 Premedications

R-ICE will be administered per standard institutional procedures with appropriate hydration and premedication per institutional standards.

### 3.5.2 Formulation, Packaging, and Storage

#### Acalabrutinib

The investigational product, acalabrutinib capsules for oral administration, is supplied as yellow and blue, opaque hard gelatin capsules, with 100 mg of acalabrutinib as the active ingredient. The capsules will be supplied by the supplier of the study medication and provided to participants at no cost. Each capsule also contains compendial inactive ingredients: silicified microcrystalline cellulose, which is composed of microcrystalline cellulose and colloidal silicon dioxide, partially pregelatinized starch, sodium starch glycolate, and magnesium stearate. The capsule shell contains gelatin, titanium dioxide, yellow iron oxide and indigotine (FD&C Blue 2).

Acalabrutinib will be provided in white, high-density polyethylene bottles.

Refer to the acalabrutinib Investigator Brochure for additional information regarding the drug product to be used in this trial.

